Buprenorphine dosing reminders. During the initial in-person training, study staff will ask participants to select at what time they will take their buprenorphine dose each day. The selected time will be programmed into the application by study staff. Then, the Video DOT+ platform will send an automatic SMS reminder to participants who have not yet submitted videos by their selected time of the day. In those instances, the following message will be displayed: “Please remember to take your buprenorphine dose.”

Reset in the incentive magnitude for a missed video or invalid buprenorphine administration. If a participant fails to submit a video or if a submitted video is deemed invalid, the participant will not receive the scheduled incentive amount that day and the daily incentive value will be decreased to \$1 per day. Then, the amount earned per day will increase to the maximum incentive value (Study 1: \$10; Study 2: \$20) after the participant submits a valid video of buprenorphine administration every day for seven days.

Reloadable credit card. At the start of enrollment, each participant will be given a reloadable credit card. After the staff member verifies that participants correctly ingested their buprenorphine dose, any incentive earnings will be added to the card. Each card can then be used as a regular credit card to make purchases at most businesses. We currently use this reloadable credit card system in our ongoing incentive programs, and it has proven very efficient and highly acceptable to participants.

Contesting the validation decision. Participants will be able to contest the validation decision of a staff monitor via the Video DOT+ application. Participants will be taught how to contest the validation

Date: February 11, 2020

Principal Investigator: [name]

Application Number: IRB00186156

decision during the in-person training and can see the decisions made on their video submissions from the application. If a participant believes that they submitted a valid video but the staff monitor marked the video as invalid, the participant can contest the result. All contested videos will be viewed by an independent staff member that was not involved in the original video validation.

Intake and Outcome Assessments

Assessments will be conducted at intake, every 4 weeks during the 24-week intervention period, and at a 12-week follow-up period. Participants will be paid \$50 for completing each of the assessments. These assessments may be collected using Qualtrics or REDCap.

Intake Only Assessment Instruments

DSM-5 Checklist for Opioid Use Disorder. The DSM-5 checklist for opioid use disorder is a structured assessment that will be used to determine if participants have opioid use disorder.

Treatment Facilitators and Barriers Questionnaire. This questionnaire will assess participants' self-reported barriers and facilitators to accessing opioid use disorder treatment.

Intake and Major Assessment Instruments

Urine toxicology testing. Urine samples will be collected under observation and tested for opioids and other drugs.

Smartphone Form. This questionnaire will document participants' access to and willingness to use a smartphone during the study.

Time-line follow-back (TLFB). Participants will be asked whether or not they are in treatment for their opioid use disorder, including treatment other than buprenorphine (e.g., methadone maintenance). For participants who report being in buprenorphine treatment, the TLFB procedure will be used to elicit participants' self-reported taking of their buprenorphine dose each day. Pharmacy and/or clinic records (with participant permission) may be used to confirm self-reported data.

Opioid Overdose Risk Assessment. An opioid overdose risk assessment will be used to assess the rate at which participants report engaging in behaviors that may put them at risk for an opioid overdose.

The Addiction Severity Index – Lite (ASI-Lite). The ASI-Lite is a structured interview designed to assess problem severity in areas commonly affected by drug and alcohol use (medical, legal, employment, family/social, and psychiatric) with good reliability and validity.

The Beck Depression Inventory (BDI). The BDI is a 21-item questionnaire designed to screen for severity of depression.

Treatment Acceptability Questionnaire. To assess the acceptability of our intervention, we will administer a Treatment Acceptability Questionnaire to participants who are exposed to our smartphone incentive intervention at the end of the 24-week intervention period.

- b. Study duration and number of study visits required of research participants.

Study participation for Study 1 and Study 2 will include a 24-week intervention evaluation period and a 12-week follow-up period for a total study duration of 36 weeks. Outcome assessments will be conducted at intake, every 4 weeks during the 24-week intervention period, and at a 12-week follow-up period.

Date: February 11, 2020

Principal Investigator: [name]

Application Number: IRB00186156

c. Blinding, including justification for blinding or not blinding the trial, if applicable.

Participants in Study 1 and Study 2 will not be blinded as to their study condition because participants in the incentive intervention cannot be blind to that intervention.

d. Justification of why participants will not receive routine care or will have current therapy stopped.

N/A

e. Justification for inclusion of a placebo or non-treatment group.

N/A

f. Definition of treatment failure or participant removal criteria.

Participants will be removed from either study if they threaten the safety of staff or other research participants, or of any other persons on the Johns Hopkins Bayview Campus.

g. Description of what happens to participants receiving therapy when study ends or if a participant's participation in the study ends prematurely.

Throughout Study 1 and Study 2, participants will be given referrals to services they might need (e.g., drug counseling, housing, medical, or employment services). Participants will continue to receive buprenorphine treatment as long as that treatment is available in the program they attend.

5. Inclusion/Exclusion Criteria

Study 1

Applicants will be invited to participate in this study if they: a) are \geq 18 years old, b) meet DSM-5 criteria for current opioid use disorder, c) provide an opioid-positive urine sample, d) report not receiving any type of drug abuse treatment in the past 30 days, and e) are interested in receiving buprenorphine treatment. Applicants will be excluded if they: a) have current suicidal/homicidal ideation, b) are pregnant or nursing, or c) are unwilling or unable to use a smartphone.

Study 2

Applicants will be invited to participate in this study if they: a) are \geq 18 years old, b) meet DSM-5 criteria for current opioid use disorder, c) provide an opioid-positive urine sample, d) report not receiving any type of drug abuse treatment in the past 30 days, and e) are interested in receiving buprenorphine treatment. Applicants will be excluded if they: a) have current suicidal/homicidal ideation, b) are pregnant or nursing, c) are unwilling or unable to use a smartphone, d) do not have access to a smartphone that can submit videos using the study smartphone app.

6. Drugs/ Substances/ Devices

a. The rationale for choosing the drug and dose or for choosing the device to be used.

Study 1

N/A

Study 2

Buprenorphine: Buprenorphine is FDA-approved for the treatment of opioid use disorder and it will be used according to that indication in this study. Participants will be offered a supervised buprenorphine induction as a part of this study. The buprenorphine induction will be open label and will follow standard clinical practice procedures. Participants will be inducted onto and maintained on buprenorphine for up to 3 weeks, or until they connect to a community buprenorphine treatment program, whichever occurs first. Participants who are maintained on buprenorphine as an outpatient will receive blister packages of sublingual buprenorphine for outpatient administration and may receive up to 24mg/day (beginning the day

Date: February 11, 2020

Principal Investigator: [name]

Application Number: IRB00186156

after induction) during this period. The highest potential dose (24mg) is below what can be administered for use on a daily basis (32mg).

Concomitant Medications: Consistent with standard clinical practice treatment, some medications will be available to participants as needed during the supervised buprenorphine induction and at discharge from the induction. The following medications may be offered during the supervised buprenorphine induction: acetaminophen (500mg, 1-2 tablets every 6 hours as needed for pain), clonidine (0.1-0.2mg every 4 hours as needed), dicyclomine (10mg every 6 hours as needed for abdominal cramps), hydroxyzine (25mg, 1-2 tablets every 8 hours as needed for anxiety), ibuprofen (600mg every 6 hours as needed for myalgia), loperamide (2mg, 1-2 tablets every 4 hours as needed for diarrhea), methocarbamol (750mg, 1 tablet every 4 hours as needed for myalgia), and ondansetron (8mg every 6 hours as needed for nausea/vomiting). The following medications may be offered at discharge from the induction: clonidine (up to four 0.1mg tablets, 1 tablet to be taken every 6 hours as needed), hydroxyzine (25mg, 1-2 tablets as needed for anxiety), ibuprofen (up to four 600mg tablets, 1 tablet to be taken every 6 hours as needed for myalgia), ondansetron (8mg, 1 tablet as needed for nausea/vomiting), and trazodone (100mg, 1 tablet as needed for sleep). These concomitant medications will be available to reduce withdrawal symptom severity during the buprenorphine induction and at time of discharge from the supervised induction.

Concomitant medications will be administered as needed per clinical recommendation and overseen by the study clinician co-investigator(s) who are conducting the supervised buprenorphine induction. Not all medications will be dispensed. The provision of these additional supportive medications may be necessary to prevent treatment attrition.

- b. Justification and safety information if FDA approved drugs will be administered for non-FDA approved indications or if doses or routes of administration or participant populations are changed.

N/A

- c. Justification and safety information if non-FDA approved drugs without an IND will be administered.

N/A

7. Study Statistics

Separate statistical analyses will be conducted for Study 1 and Study 2. We will compare the Usual Care Control and Video DOT+ groups on primary and secondary outcome measures. To preserve statistical power and minimize the likelihood of endorsing false conclusions, we identified one primary outcome measure and several secondary outcome measures, each associated with a *Specific Aim*.

- a. Primary outcome variable.

Study 1 and Study 2 have the same primary outcome:

Specific aim. *Assess efficacy of Video DOT+ in promoting buprenorphine treatment adherence as assessed by urine drug screens.* We will assess the percentage of participants with buprenorphine-positive urine samples at the 4-week assessments during the 24-week intervention evaluation period (Yes/No at each assessment). Hypothesis: We expect that Video DOT+ participants will have more buprenorphine-positive urine samples during the 24-week intervention relative to the Usual Care Control participants.

- b. Secondary outcome variables.

Study 1 and Study 2 have the same secondary outcomes:

Specific aim. *Assess efficacy of Video DOT+ in promoting self-reported buprenorphine treatment*

Date: February 11, 2020

Principal Investigator: [name]

Application Number: IRB00186156

adherence. We will assess the number of days participants report taking their daily buprenorphine dose during the 30 days prior to each of the 4-week assessments during the 24-week intervention evaluation period (based on TLFB). *Hypothesis:* We expect that Video DOT+ participants will have more days of taking their buprenorphine dose as prescribed during the 24-week intervention relative to the Usual Care Control participants.

Specific aim. Assess efficacy of Video DOT+ in promoting linkage to buprenorphine treatment. We will assess the percentage of participants who link to buprenorphine treatment during the 24-week intervention evaluation period (Yes/No, based on self-report and medical records). *Hypothesis:* We expect that more Video DOT+ participants will link to buprenorphine treatment during the 24-week intervention relative to the Usual Care Control participants.

Specific aim. Assess efficacy of Video DOT+ in promoting retention in buprenorphine treatment. We will assess the total number of days participants are in buprenorphine treatment from the time of randomization until the last day of medication during the 24-week intervention evaluation period (based on self-report and medical records). *Hypothesis:* We expect that Video DOT+ participants will be retained in buprenorphine treatment for more days during the 24-week intervention relative to the Usual Care Control participants.

Specific aim. Assess efficacy of Video DOT+ in reducing opioid use. We will assess the percentage of participants with opioid-positive urine samples (excluding buprenorphine and methadone if self-report and medical records confirm that the participant is enrolled in buprenorphine or methadone treatment) at the 4-week assessments during the 24-week intervention evaluation period (Yes/No at each assessment).

Hypothesis: We expect that Video DOT+ participants will have fewer opioid-positive urine samples during the 24-week intervention relative to the Usual Care Control participants.

Specific aim. Assess efficacy of Video DOT+ in reducing risk of opioid overdose. We will assess the rates at which participants report engaging in overdose risk behaviors at the 4-week assessments during the 24-week intervention evaluation period (based on total scores from the opioid overdose risk assessment).

Hypothesis: We expect that Video DOT+ participants will engage in lower rates of opioid overdose risk behaviors during the 24-week intervention relative to Usual Care Control.

Specific aim. Assess efficacy of Video DOT+ in promoting buprenorphine treatment engagement and adherence, and reducing opioid use and risk of opioid overdose after the intervention ends. We will assess these outcomes at the 12-week follow-up after the intervention ends. *Hypothesis:* We expect that Video DOT+ participants will have better buprenorphine treatment outcomes relative to the Usual Care Control participants after the intervention ends.

c. Statistical plan including sample size justification and interim data analysis.

Statistical Analyses

Separate statistical analyses will be conducted for Study 1 and Study 2, using the procedures described below.

We will analyze measures assessed repeatedly over time with a longitudinal logistic regression model. Within-person correlated outcomes will be handled using generalized estimating equations (GEE; Zeger, Liang, & Albert, 1988). Measures assessed once will be analyzed using logistic regression. The magnitude of effects will be expressed using odds ratios with 95% confidence intervals. Retention in buprenorphine treatment during the 24 weeks of the intervention period will be analyzed with a Cox proportional hazards model. We will adjust the intent-to-treat analyses for covariates used for stratification (Pocock, Assmann, Enos, & Kasten, 2002). Tests will be two-sided and, because we have one primary outcome, alpha will be set at 0.05.

Primary outcome analyses. The primary outcome measure will be the percentage of participants with buprenorphine-positive urine samples at the 4-week assessments during the 24-week intervention

Date: February 11, 2020

Principal Investigator: [name]

Application Number: IRB00186156

[figure not shown]
evaluation period (Y/N at each assessment). We will fit a longitudinal logistic regression model $\text{logit}(Y_{ij}) = \beta_0 + \beta_1 tx + \beta_2 \cdot 3x_{2-3} + \varepsilon_{ij}$, where Y_{ij} is evidence of buprenorphine adherence for the i th person at the j th timepoint (6 visits over 24 weeks), β_1 is the covariate of interest representing the expected increase in log odds of evidence of buprenorphine adherence as a function of assignment to the treatment group, and β_2 are the coefficients for the 2 randomization covariates. We will fit models with time and time by treatment interactions secondarily. These models will allow us to look at change over time in buprenorphine adherence in each study arm.

Secondary outcome analyses. We will fit longitudinal logistic regression models, similar to those described for the primary outcome measure, for self-reported buprenorphine treatment adherence, opioid use, and opioid overdose risk behaviors. Linkage to buprenorphine treatment and post-intervention effects will be assessed by logistic regression. Retention in buprenorphine treatment during the 24 weeks of the intervention period will be analyzed with a Cox proportional hazards model.

Missing data. We expect to collect $\geq 85\%$ of the study assessments. Our primary approach to handle missing data will be to impute missing values as the adverse outcome (e.g., buprenorphine-negative urine sample). Model parameter estimates from this approach will be compared to a method without imputation. If these methods yield differing results, conclusions will need to be tentative, but results from both approaches will be reported in publications. To investigate sensitivity to missing values, participants with and without missing values will be compared by covariates and group assignment. If rates are higher than expected, we may use mixed effects models rather than GEE estimation, as the former has less strict assumptions regarding missing data (missing at random, rather than missing completely at random). If the data are missing not at random, then we will fit pattern mixture models as described by Hedeker and Gibbons (1997).

Power Analyses

We used Liu and Liang (1997) to determine the number of participants required to detect a difference between groups with 80% power. The adjacent figure shows the total number of participants (N) that would be required to detect a difference of 25% between the Usual Care Control and Video DOT+ groups with the six assessments during the 24-week intervention period. The figure shows different percentages for the Usual Care Control group because that value affects the sample size required. Twenty-five percent is smaller than the increase produced in our prior study of incentives to promote daily adherence to oral naltrexone in opioid-dependent adults (Dunn et al., 2013). It is also smaller than the incentive effects in promoting drug abstinence, medication adherence, and other health behaviors as shown in three different meta-analyses (Petry et al., 2012; Prendergast et al. 2006; Lussier et al., 2006). Based on this, we need to randomize 64 participants (horizontal dashed line) to detect a difference between the Usual Care Control and the Video DOT+ groups on the primary outcome measure.

d. Early stopping rules.

The PI ([name], PhD) and two co-investigators at Johns Hopkins University School of Medicine ([name], PhD; [name], MD) will provide data and safety monitoring of the proposed studies. To monitor adverse events, all staff members who have regular contact with study participants are instructed on the need to report to an investigator any indication that an adverse event has occurred. When

Date: February 11, 2020

Principal Investigator: [name]

Application Number: IRB00186156

the staff members and investigators learn of an adverse event, they will investigate until they have determined as many of the relevant details of the adverse event as possible. To provide consistent monitoring of adverse events across groups, participants will be asked about all categories of adverse events at each routine assessment visit conducted throughout the studies. At least one investigator will review each adverse event as it occurs. All investigators will review a summary of adverse events at the time of the annual reports to the IRB. This frequency of review will be increased if the adverse events occur at a higher rate than anticipated. The protocol can be stopped based on recommendations of the investigators who are reviewing the adverse events in the studies. We will ask the investigators to recommend that the trial be stopped if a review of the adverse events suggests to any of the investigators that the number of related adverse events is unacceptably high. The investigators will be allowed to request statistical analyses to compare the groups on the rates of different adverse events or to have the adverse event data summarized in other ways that they deem appropriate.

8. Risks

a. Medical risks, listing all procedures, their major and minor risks and expected frequency.

This study involves the development and evaluation of a behavioral intervention to promote uptake of and adherence to an FDA-approved medication (sublingual buprenorphine) for opioid use disorder. Buprenorphine has very few contraindications, but is not recommended for use with the opioid antagonist naltrexone or other opioid agonists. It is rated in pregnancy category C, therefore all women who are pregnant or nursing will be excluded from study participation. Buprenorphine's side effects are minimal and rare (hyperhidrosis 14%, abdominal pain 11%, constipation 12%, nausea 15%, headache 37%, insomnia 14%) and overlap significantly with known opioid withdrawal symptoms (e.g., abdominal pain, nausea). It is expected that participants may experience some level of opioid withdrawal. Symptoms of opioid withdrawal include nausea, diarrhea or stomach cramping, muscle aches and pains, yawning, sweating, pupil dilation, minor increases in blood pressure, and runny nose/tearing eyes. To help to alleviate these symptoms, the study clinician co-investigator(s) who are conducting the supervised buprenorphine induction may offer participants the concomitant medications listed in Section 6.

The study poses little risk to participants and offers the potential of substantial benefit. There is essentially no risk above those of normal daily living associated with the incentives, or with the data collection procedures proposed in this study.

b. Steps taken to minimize the risks.

To protect confidentiality, all research participants are identified by participant identification codes (Participant IDs) consisting of their initials and sequentially-assigned participant numbers on most forms and data files, and not by their names. All research data are stored in locked areas accessible only to research staff and are not left unattended. Documents with confidential information are shredded before being discarded. Confidential information is never given to anyone outside of the research program without the explicit written permission of the research participant. Only selected designated staff members are approved to give confidential information out after obtaining explicit written permission from the participant. All research staff are trained in these procedures. We collect only general information about participant activities, legal and illegal. We do not collect information about specific illegal acts. Finally and importantly, the Video DOT+ application that will be used to provide monitoring of adherence and incentives has features that promote compliance with HIPAA.

Buprenorphine has been approved for use by the FDA and our study will conform to the FDA guidelines. Participants will be referred to our collaborating primary care providers to receive buprenorphine treatment. In addition, the exclusion criteria were selected to minimize the risks associated with buprenorphine treatment. If a participant becomes pregnant while in the study, she will be referred for

Date: February 11, 2020

Principal Investigator: [name]

Application Number: IRB00186156

medical treatment in an appropriate medical clinic (e.g., a specialty clinic for pregnant women who abuse drugs).

c. Plan for reporting unanticipated problems or study deviations.

Unanticipated problems or study deviations will be reported based on the guidelines of the Johns Hopkins University School of Medicine IRB.

d. Legal risks such as the risks that would be associated with breach of confidentiality.

There are risks that the confidential information we collect could be revealed to people not involved in the research such as a friend, relative, or an outside organization. This could be embarrassing to the participant if the participant wanted to keep participation in the study secret. The legal risks are limited because we collect only general information about participant activities, legal and illegal. We do not collect information about specific illegal acts. Thus, the risks associated with the assessments are not greater than the risks associated with routine psychological examinations or tests.

e. Financial risks to the participants.

There are no financial risks above those of normal daily living. Each participant is responsible for ensuring that the earnings are reported properly to relevant government or private agencies and for determining whether or not the earnings will affect any benefits they might receive from those agencies.

9. Benefits

a. Description of the probable benefits for the participant and for society.

All participants will be offered referrals to buprenorphine treatment, which could help to reduce their opioid use and risk of opioid overdose death. Participants in the experimental group will receive access to our customized mobile-health application that could facilitate adherence to buprenorphine treatment. If the proposed intervention is an effective means of promoting buprenorphine treatment engagement and adherence, it could reduce the substantial morbidity, mortality, and societal healthcare costs associated with untreated opioid use disorder.

10. Payment and Remuneration

a. Detail compensation for participants including possible total compensation, proposed bonus, and any proposed reductions or penalties for not completing the protocol.

All incentives in this study will be provided by giving participants reloadable credits and adding incentives to the card when earned. We have been using these reloadable credit cards in our ongoing research and they have proved attractive to participants and convenient for staff to manage. Payment for participating in Study 1 and Study 2 are described in detail below.

Study 1

Incentives for taking and completing a computer-based education program. Participants will be invited to participate in a computer-based training program. Participants may earn up to \$10 for completing the Knowledge Tests and may earn up to about \$33 for participating in the computer-based training.

Incentives for completing routine assessments for both groups. Outcome assessments will be conducted at intake, every 4 weeks during the 24-week intervention period, and at a 12-week follow-up period. Participants will be paid \$50 for completing each of the assessments.

Participant referral fees. As in our previous studies, participants will have the optional opportunity to earn incentives for referring people who are interested in the study. If a referral attends the initial screening appointment and completes the necessary assessments, the participant who referred the person will receive

Date: February 11, 2020

Principal Investigator: [name]

Application Number: IRB00186156

up to \$20. If a referred person enrolls in the main study, the participant who referred the person will receive up to \$40 for making the referral.

Incentive for linkage to buprenorphine treatment. Prior to earning incentives for buprenorphine treatment adherence, participants in the Video DOT+ group will be able to earn \$70 for documenting that they have an active prescription for buprenorphine.

Video DOT+ for facilitating sublingual buprenorphine adherence. Participants in the Video DOT+ group will be able to earn \$10 per day for taking their buprenorphine dose and submitting a valid video recording of administration before midnight. Over the entire 24-week study period, participants in the Video DOT+ group could earn \$1,680 for adhering to buprenorphine treatment.

Study 2

Incentives for taking and completing a computer-based education program. Participants will be invited to participate in a computer-based training program. Participants can earn \$30 for completing the computer-based training.

Incentives for completing routine assessments for both groups. Outcome assessments will be conducted at intake, every 4 weeks during the 24-week intervention period, and at a 12-week follow-up period. Participants will be paid \$50 for completing each of the assessments.

Participant referral fees. As in our previous studies, participants will have the optional opportunity to earn incentives for referring people who are interested in the study. If a referral attends the initial screening appointment and completes the necessary assessments, the participant who referred the person will receive up to \$20. If a referred person enrolls in the main study, the participant who referred the person will receive up to \$40 for making the referral.

Incentive for linkage to buprenorphine treatment. Participants can earn \$70 for participating in the supervised buprenorphine induction and \$70 if they obtain a buprenorphine prescription from a community program.

Video DOT+ for facilitating sublingual buprenorphine adherence. Participants in the Video DOT+ group will be able to earn \$20 per day for taking their buprenorphine dose and submitting a valid video recording of administration before midnight. Over the entire 24-week study period, participants in the Video DOT+ group could earn \$3,360 for adhering to buprenorphine treatment.

11. Costs

- a. Detail costs of study procedure(s) or drug (s) or substance(s) to participants and identify who will pay for them.

There will be no costs to participants for any services or treatment provided in this study.

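### Secondary outcomes: the opioid-use rule scores enrolled participants as opioid-positive for taking treatment when no record confirms enrolment, record checks are optional, and the error can differ by arm

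*Combined protocol and SAP*

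**What the plan says.** Section 7b defines opioid use as the percentage of participants with opioid-positive urine at the 4-weekly assessments, "excluding buprenorphine and methadone if self-report and medical records confirm that the participant is enrolled in buprenorphine or methadone treatment". The default is thus to count both drugs. They are set aside only when both sources agree that the participant is enrolled.

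The time-line follow-back paragraph in Section 4 has every participant asked about current treatment, including treatment other than buprenorphine. It then says: "Pharmacy and/or clinic records (with participant permission) may be used to confirm self-reported data".

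Linkage in Section 7b is "Yes/No, based on self-report and medical records". Retention draws on the same two sources.

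Section 10, Study 1, describes a $70 payment: "Prior to earning incentives for buprenorphine treatment adherence, participants in the Video DOT+ group will be able to earn" it "for documenting that they have an active prescription for buprenorphine". Section 4 gives Usual Care the standard services and referrals, with no such payment. For Study 2, Section 4 lists the linkage payments under the Video DOT+ heading, while Section 10 names no arm. The payment asymmetry is therefore claimed here for Study 1 only.

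On missing data, Section 7c says: "Our primary approach to handle missing data will be to impute missing values as the adverse outcome". It adds: "Model parameter estimates from this approach will be compared to a method without imputation". It also promises a comparison of participants with and without missing values by group, and tentative conclusions with both results reported if the two methods differ.

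**The concern.** Section 7b makes a record decisive for scoring a urine sample, and Section 4 leaves obtaining that record to discretion and consent. Where the record is not obtained, a participant doing what the trial hopes for, taking prescribed buprenorphine and no other opioid, is counted as using opioids. Buprenorphine in someone who truly is not enrolled is meant to count, and is not the problem here.

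Two features let the error differ between arms. Section 7b expects Video DOT+ to have more buprenorphine-positive samples, so more of its samples are exposed to the rule. In Study 1 only Video DOT+ participants have a paid reason to produce a prescription, so enrolment may be confirmed more often there. These pull in opposite directions.

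The payment is part of the intervention, and any true rise in linkage that it causes is a legitimate effect. What is at stake is whether the secondary comparisons of opioid use, and possibly linkage, measure behaviour or partly measure paperwork.

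**Working it through.** The plan gives no confirmation rates and no figure for this point, so there is nothing to reproduce. All rates below are assumptions, used to show range and sign.

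**1. What the rule does to one sample.** Take an enrolled participant whose urine is positive for buprenorphine only.
- Self-report and record both confirm enrolment: buprenorphine is excluded and the sample is negative.
- Self-report says enrolled, no record obtained: the condition is not met and the sample is opioid-positive.

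In the second case the sample is observed and scored. It is not a missing value, so the missing-data checks in Section 7c would not flag it.

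**2. Opioid use, effect on the comparison.** Let q be the share of samples positive only for buprenorphine or methadone from enrolled participants, and u the share of those without a confirming record (c = control, t = Video DOT+). Each arm's opioid-positive rate is overstated by q × u.

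Spurious difference in favour of Video DOT+ = q_c × u_c − q_t × u_t.

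Assumed ranges: q_c 10–20%, q_t 15–40%, u_c 20–50%, u_t 10–20%, with q_t ≥ q_c and u_t ≤ u_c.
- Minimum: 0.10 × 0.20 − 0.40 × 0.20 = −0.060
- Maximum: 0.20 × 0.50 − 0.20 × 0.10 = +0.080
- Equal exposure, better records in Video DOT+: 0.15 × 0.50 − 0.15 × 0.10 = +0.060
- Equal records, more exposure in Video DOT+: 0.15 × 0.20 − 0.40 × 0.20 = −0.050
- Equal on both: 0.15 × 0.20 − 0.15 × 0.20 = 0

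The fourth line shows that equal record checking alone does not remove the error when exposure differs.

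The $70 covers one buprenorphine prescription. It documents neither methadone treatment nor enrolment at each visit, so it bears only partly on this outcome.

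**3. Linkage, conditional.** Suppose (a) the document submitted for the $70 is used as linkage evidence and (b) self-report without a record is coded as unlinked. With the same true linkage L in both arms and confirmation probabilities s_t and s_c, the false difference is L × (s_t − s_c).
- L = 60%, 95% vs 75%: 0.60 × 0.20 = 12 points
- L = 60%, 95% vs 85%: 0.60 × 0.10 = 6 points
- L = 40%, same pairs: 8 and 4 points
- Self-report suffices, or confirmation is equal: 0

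If Section 7c's procedures cover missing records, the 12-point case would show 0.60 × 0.05 = 3% vs 0.60 × 0.25 = 15% missing by group. Dropping only the unconfirmed self-reported links gives 0.57/0.97 = 58.8% vs 0.45/0.85 = 52.9%, a gap of 5.8 points. If records are missing equally for linked and unlinked people, the gap is 0.

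**4. False-positive rate, illustration only.** Study 1's size per arm is not stated. The power section gives 64 to randomize without tying it to a study. The opening abstract gives 105, read here as the total across both studies. Half of 64 is 32; the remainder, 105 − 64 = 41, splits 20 and 21. Exact enumeration of an unadjusted pooled two-proportion z-test at |z| > 1.96 (the plan itself uses covariate-adjusted logistic regression):

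| Observed linkage | 32 per arm | 20 and 21 |
|---|---|---|
| 60% vs 60% | 5.6% | 5.6% |
| 57% vs 45% | 18.1% | about 14% |
| 57% vs 51% | 8.9% | about 8% |

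**The case against.** The strongest reply is that Section 7b already makes records part of the outcome definitions, and that the permissive wording sits in one instrument paragraph that applies to both arms. Treatment status is asked of everyone, at assessments paid $50 in both arms. That is fair, and it means nothing in the plan makes record checks arm-specific by design. It does not remove the contradiction: a rule that needs a record cannot be applied as written where the record is optional and may be refused. Study-held prescribing and Study 2 induction records may narrow the gap, but they do not cover care from community providers.

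A reader might infer that linkage is biased toward Video DOT+. The documents do not support that. They do not say that the paid-for document feeds the linkage variable, or that an unconfirmed self-report counts as unlinked. Adverse-outcome imputation could produce that coding, but it is written for missing values, with a urine sample as its example. If it did cover records, the non-imputed comparison, the comparison by group and the promise of tentative conclusions would partly expose the gap.

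A reader might also infer that the opioid-use error must favour Video DOT+. That holds only if both arms have the same share of treatment-only samples, and the plan's own hypothesis expects otherwise.

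**Conclusion.** The point holds for the secondary opioid-use outcome. Followed as written, the plan can classify treatment as opioid use, by an amount that may differ between arms and that its missing-data checks would not detect. Over the assumed ranges the net effect is −6 to +8 points, so neither sign nor size is established. Bias is possible, not demonstrated.

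For linkage the concern is conditional on the two unstated assumptions, and is zero if self-report suffices. The false-positive figures illustrate an assumed gap at an assumed sample size and should not be quoted as a property of the trial. Retention shares the data sources, but the link is indirect and no size is claimed. The primary outcome, buprenorphine-positive urine, needs no confirmation of enrolment and is untouched. Severity is minor to moderate.

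**What to change.** Reconcile the optional record checks in Section 4 with the outcome definitions in Section 7b that rely on records, and make two changes.

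1. Seek record releases from all participants at intake, and query the same sources, including study-held prescribing and induction records, on the same schedule in both arms. Do not use the document submitted for the $70 as outcome evidence unless equivalent evidence is sought from controls.
2. Keep the Section 7b definition of opioid use, and pre-specify an added analysis that counts only opioids other than buprenorphine and methadone in every sample. Tabulate unconfirmed buprenorphine-only and methadone-only samples by arm.

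The second change is needed as well as the first because equal record checking still leaves an error when exposure differs between arms. The cost is low: uniform requests where record checks are already foreseen, one analysis and one table. The downside is that the added analysis does not count non-prescribed buprenorphine or methadone, which matters in a trial concerned with diversion. It should accompany the current definition, not replace it.
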